The proposed single dose levels will be 30 mg, 60 mg, 120 mg and 150 mg, although they may change with emerging data from this study. The top dose will be no higher than 150 mg as this is the maximum dose that was administered to healthy volunteers in the AstraZeneca Global SAD/MAD Study (AstraZeneca Protocol Number: D0520C00001 “A Phase I, Randomised, Double Blind, Placebo Controlled, 2-part Study to Assess the Safety, Tolerability and Pharmacokinetics of Single and Multiple Oral Doses of AZD9668 in Healthy Volunteers” Date: [REDACTED]) and was found to be safe. In addition, modelled PK data from the current study will ensure that the predicted geometric mean C_{max} and $AUC_{(0-24)}$ at the top dose will not exceed 2.5 μM or 18 $\mu\text{M}\cdot\text{h}$, respectively. The multiple doses for both cohorts 1 and 2 will be selected following a safety review meetings using emerging data from the current study and the AstraZeneca Global SAD/MAD Study The maximum multiple dose will be capped at a total daily dose of 140 mg. In addition, the emerging PK data from the current study will be modelled to ensure that for the highest dose given, the predicted geometric mean exposures (both $AUC_{(0-24),ss}$ and $C_{max,ss}$) will not exceed 2.5 μM or 18 $\mu\text{M}\cdot\text{h}$, respectively.

Duration of treatment

For each cohort of volunteers, the study will last a minimum of four weeks.

Variables

- Pharmacokinetic

Plasma concentration of AZD9668 is a primary outcome variable and concentration of AZD9668 in urine is a secondary outcome variable.

From these data, the following PK parameters will be derived:

Single dose - Day 1 and 7: C_{max} ; t_{max} ; $AUC_{(0-t)}$; AUC ; $AUC_{(0-12)}$; $AUC_{(0-24)}$; $t_{1/2}$; V_z/F ; CL/F ; CL_R ; A_e ; F_e

Multiple dose - Day 13: C_{max} ; t_{max} ; $AUC_{(0-12)}$; C_{12} ; A_e ; F_e . The A_e and F_e will be estimated using data from 0-12 hours

Day 19: $C_{min,ss}$; $C_{max,ss}$; $t_{max,ss}$; $AUC_{(0-t),ss}$; $AUC_{(0-12),ss}$; $AUC_{(0-24),ss}$; $AUC_{,ss}$; $V_z/F_{,ss}$; $CL/F_{,ss}$; $t_{1/2,ss}$; CL_R ; $A_{e,ss}$; $F_{e,ss}$; R_{ac} ; $C_{12,ss}$

- Pharmacodynamic

The PD outcome variables for AZD9668 are as follows:

Single and multiple dosing – Inhibition of NE activity following zymosan stimulation *ex vivo*.

- Safety

The safety outcome variables for AZD9668 are primary variable, and are as follows:

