Appendix A Signatures

Appendix B Additional Safety Information

LIST OF SUPPLEMENTS

Supplement N/A

LIST OF ABBREVIATIONS AND DEFINITION OF TERMS

The following abbreviations and special terms are used in this study protocol.

Abbreviation or special term	Explanation
α 1-AT	Alpha 1 – antitrypsin
ACM	Ambulatory cardiac monitoring
A_e	Cumulative amount of unchanged drug excreted into urine
$A_{e,ss}$	A_e at steady state
AE	Adverse event
ALT	Alanine aminotransferase
AMC	7-amino 4-methyl coumarin
AST	Aspartate aminotransferase
ATC	Anatomical therapeutic chemical classification of drug
AUC	Area under the plasma concentration time curve from time zero to infinity
$AUC_{,ss}$	AUC at steady state
$AUC_{(0-t)}$	AUC from time zero to a specified time
$AUC_{(0-t),ss}$	$AUC_{(0-t)}$ at steady state
AZDD	AstraZeneca drug dictionary
BAL	Bronchoalveolar lavage
BMI	Body mass index
C_{12}	Concentration at 12 hours post dose
$C_{12,ss}$	C_{12} at steady state
[REDACTED]	[REDACTED]
CEFTS	Central ECG files transfer and storage; the AstraZeneca central dECG repository
CGG	Clinical genotyping group
CL/F	Apparent plasma clearance following oral drug administration
$CL/F_{,ss}$	CL/F at steady state
CL_R	Renal clearance of drug from plasma
C_{max}	Observed peak or maximum plasma concentration following drug administration
$C_{max,ss}$	C_{max} at steady state

Abbreviation or special term	Explanation
$C_{\min,ss}$	Minimum plasma (trough) drug concentration after repetitive dosing after steady state is achieved, prior to the first dose of the study day
COPD	Chronic obstructive pulmonary disease
CPK	Creatinine phosphokinase
CPMP	Committee for Proprietary Medicinal Products
CPU	Clinical pharmacology unit
CRF	Case report form
CSR	Clinical study report
DMPK	Drug metabolism and pharmacokinetics
DNA	Deoxyribonucleic acid
[REDACTED]	[REDACTED]
dECG	Digital ECG
ECG	Electrocardiogram
Ecode	Enrolment code
EDTA	Ethylenediamine tetra-acetic acid
Ethics Committee	Synonymous to Institutional Review Board and Independent Ethics Committee
EU	European Union
F_e	Fraction of dose excreted unchanged in the urine
$F_{e,ss}$	F_e at steady state
FSH	Follicle stimulating hormone
GCP	Good clinical practice
GGT	Gamma glutamyltransferase
GMP	Good manufacturing practice
HDPE	High-density polyethylene
HELC	Human Exposure Limits Committee
hERG	Human-ether-a-go-go gene
HIV	Human immunodeficiency virus
HR	Heart rate
HRT	Hormone replacement therapy
hsCRP	High sensitivity C-reactive protein

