3. STUDY PLAN AND PROCEDURES

3.1 Overall study design

This Clinical Study Protocol has been subjected to a peer review according to AstraZeneca standard procedures.

This is double blind, randomised, placebo controlled, parallel group, Phase 1 study. Up to four single dose levels, and two multiple dose levels will be studied in two Japanese and two Caucasian cohorts, each comprising of eight healthy volunteers: In each cohort, two single dose levels, and one multiple dose level will be studied, each separated by a washout period (minimum of 7 days), with the intention that parallel cohorts of Japanese and Caucasian healthy volunteers (age and sex matched) are studied concurrently.

Each volunteer will receive two ascending single doses once daily (on Days 1 and 7), followed by multiple doses (twice daily each dose administered 12 hours apart) for 6 days (Days 13-18), and a final single dose on the morning of Day 19 (ie, a total of 15 doses).

Cohorts of Japanese and Caucasian volunteer will receive the same dose of AZD9668, and will be run in parallel as far as is possible.

The intention is that volunteers remain resident in the [REDACTED] from Day -1 until approximately 72 hours after each of the single doses and after the last dose in Visit 4 (ie, from Day -1 to Day 4; Day 6 to Day 10; and Day 12 to Day 22). The volunteers will be allowed home in between the single doses or may stay in the unit at the Investigators discretion. If the dosing schedule is separated further for practical reasons, volunteers will be allowed home, from approximately 72 hours after the last dose in each treatment period. (Note - Further separation of the dosing periods will not affect the 'study day' nomenclature).

Figure 1 shows the study flow chart and Table 1 outlines the assessments at each visit.

Visit 1a (to provide informed consent only) and Visit 1b (enrolment and screening) will take place up to 21 days prior to Visit 2.

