⁷ Telemetry from -1 to 24 hrs post-dose at Visits 2, 3 and 4, and from -1 to 24 hrs post dose on Day 19 (Visit 4).

⁸ Vital signs will be measured at the timepoints shown in Table 2.

⁹ Female volunteers only.

¹⁰ PK sampling times are detailed in Table 3.

¹¹ Urine collections: Pre-dose on Days 1, 7 and 13 and post dose at 0-4, 4-8, 8-12, 12-24, 24-36, 36-48 hrs on Days 1, 7 and 19. On Day 13 at 0-4, 4-8, 8-12 hrs post dose.

¹² Pharmacodynamic (PD) blood sampling times are shown in Table 4.

¹³ Pharmacogenetic (PGx) blood sample to be obtained at any suitable timepoint post dose.

Table 2 ECG and vital signs assessment schedule – Visits 2, 3 and 4

Time (Relative to dosing)
-01:00
00:00
00:30
01:00
01:30
02:00
03:00
04:00
06:00
08:00
12:00
24:00

Paper ECGs, dECGs (if required), and vital signs (ie, sitting blood pressure and pulse) will be performed at the above times at Visits 2 and 3 (single doses) and after the first and last multiple doses (ie on Days 13 and 19 [Visit 4]). Paper ECGs will also be measured at 48 and 72 hours post dose at Visits 2, 3 and 4.

Table 3 Pharmacokinetic sampling schedule

Day	Time (hours - relative to dosing)
1	Pre-dose, 0.25, 0.5, 1, 2, 3, 4, 5, 7, 9, 12, 24, 36, 48, 72 post-dose
7	Pre-dose, 0.25, 0.5, 1, 2, 3, 4, 5, 7, 9, 12, 24, 36, 48, 72 post-dose
13	Pre-dose, 0.25, 0.5, 1, 2, 3, 4, 5, 7, 9, 12 (pre-dose 2), 13, 15 post-dose
14 and 15	Pre-dose (dose 1)
16 and 17	Pre-dose (dose 1), 1 post-dose
18	Pre-dose (dose 1)
19	Pre-dose, 0.25, 0.5, 1, 2, 3, 4, 5, 7, 9, 12, 24, 36, 48, 72 post-dose

Table 4 Pharmacodynamic sampling schedule

Day	Time (hours - relative to dosing)	
	Cohort 1	Cohort 2
1	Pre-dose, 1, 24 post-dose	Pre-dose, 1, 48 post-dose
7	Pre-dose, 1, 48 post-dose	Pre-dose, 1, 48 post-dose
13	Pre-dose (dose 1), 1 post-dose	Pre-dose (dose 1), 1 post-dose

Time (hours - relative to dosing)		
19	Pre-dose, 1, 24 post-dose	Pre-dose, 1, 48 post-dose

Total of 11 blood samples per volunteer in each cohort.

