The proposed single dose levels are 30 mg, 60 mg, 120 mg and 150 mg, although they may change with emerging data from this study. The top dose will be no higher than 150 mg as this is the maximum dose that was administered to healthy volunteers in the AstraZeneca Global SAD/MAD Study and was found to be safe. In addition, modelled PK data from the current study will ensure that the predicted geometric mean C_{max} and $AUC_{(0-24)}$ at the top dose will not exceed 2.5 μM or 18 $\mu\text{M}\cdot\text{h}$, respectively. The multiple doses for both cohorts 1 and 2 will be selected following a safety review meetings using emerging data from the current study and the AstraZeneca Global SAD/MAD Study. The maximum multiple dose will be capped at a total daily dose of 140 mg. In addition, the emerging PK data from the current study will be modelled to ensure that for the highest dose given, the predicted geometric mean exposures (both $AUC_{(0-24),ss}$ and $C_{max,ss}$) will not exceed 2.5 μM or 18 $\mu\text{M}\cdot\text{h}$, respectively.

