6.1.1.1 Single dosing

The PK parameters will be calculated using non-compartmental analysis. The PK parameters measured at Day 1 and Day 7 include:

Maximum plasma drug concentration (C_{max}), time to maximum plasma drug concentration (t_{max}), area under the (plasma drug concentration-time) curve from time zero to time t ($AUC_{(0-t)}$), area under the (plasma drug concentration-time) curve from time zero to infinity (AUC), AUC from time zero to 12 hours ($AUC_{(0-12)}$), AUC from time zero to 24 hours ($AUC_{(0-24)}$), terminal half-life of drug in plasma ($t_{1/2}$), apparent terminal volume of distribution following oral drug administration (Vz/F), apparent plasma clearance following oral drug administration (CL/F), renal clearance (CL_R), cumulative amount excreted in urine (A_e), and fraction of dose excreted unchanged in the urine (F_e).

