6.1.1.2 Multiple dosing

Day 13: C_{max} ; t_{max} ; $AUC_{(0-12)}$; concentration at 12 hours post dose (C_{12}); A_e ; F_e . The A_e and F_e will be estimated using data from 0-12 hours

Day 19: Minimum plasma (trough) drug concentration after repetitive dosing after steady state is achieved, prior to the first dose of the study day ($C_{min,ss}$), C_{max} at steady state ($C_{max,ss}$), t_{max} at steady state ($t_{max,ss}$), $AUC_{(0-12)}$ at steady state ($AUC_{(0-12),ss}$), $AUC_{(0-24)}$ at steady state ($AUC_{(0-24),ss}$), AUC at steady state (AUC_{ss}), Vz/F at steady state (Vz/F_{ss}), CL/F at steady state (CL/F_{ss}), $t_{1/2}$ at steady state ($t_{1/2,ss}$), CL_R , A_e at steady state ($A_{e,ss}$), F_e at steady state ($F_{e,ss}$), accumulation ration (R_{ac}), C_{12} at steady state ($C_{12,ss}$)

The R_{ac} will be calculated using the following equation:

$$R_{ac} = AUC_{(0-12),ss} \text{ Day 19} / AUC_{(0-12)} \text{ Day 13}$$

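### Day 19 carries one morning dose of a twice-daily regimen, so AUC(0-24),ss as the protocol defines it understates 24-hour steady-state exposure

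*Protocol*

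**What the plan says.** **Dosing.** Protocol section 3.1 gives single doses on Days 1 and 7, then doses 12 hours apart on Days 13-18, "and a final single dose on the morning of Day 19 (ie, a total of 15 doses"). The same section calls the Day 19 dose the last one and keeps volunteers resident for about 72 hours after it.

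**Sampling.** In Table 3 the Day 13 row marks the second dose: "12 (pre-dose 2), 13, 15 post-dose". The Day 19 row runs from pre-dose to 72 h with no such mark.

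**Parameter.** The synopsis and section 6.1.1.2 both list AUC(0-24),ss for Day 19, beside AUC(0-12),ss. Section 6.1.1.2 expands it only as AUC(0-24) at steady state. The list of abbreviations defines AUC(0-t) as "AUC from time zero to a specified time", and section 6.1.1.1 defines AUC(0-24) as the area from zero to 24 hours. No rule doubles AUC(0-12),ss or adds the missing dose.

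**Exposure limit.** The synopsis and sections 3.1, 3.2.1 and 3.4.2 say that "the predicted geometric mean exposures (both $AUC_{(0-24),ss}$ and $C_{max,ss}$) will not exceed" the stated limits. From the units, the AUC limit is 18 µM.h. Section 3.1.1.3 puts the same limit in the multiple-dose stopping rule. Section 3.1 adds: "The maximum multiple dose will be capped at a total daily dose of 140 mg".

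**The concern.** A 24-hour steady-state area on a 12-hourly regimen should contain two doses. The Day 19 window contains one, and from 12 to 24 h the drug is only washing out. Following the protocol's definitions therefore reports a post-last-dose area under a steady-state label. It does so under the primary PK objective, on the regimen that section 3.2.1 says is planned for patient studies.

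The symbol also serves two purposes. In the 18 µM.h limit it should mean exposure over a day with two doses. On Day 19 it means exposure over a day with one. Section 3.1 has the Safety Review Committee use cohort 1 multiple-dose PK when confirming the cohort 2 multiple dose. If the observed Day 19 value were scaled at that point, the margin to the limit would look wider than it is.

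**Working it through.** **1. Dose count.** 1 (Day 1) + 1 (Day 7) + 6 x 2 (Days 13-18) + 1 (Day 19) = 15, the protocol's own total. An evening dose on Day 19 would make 16.

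**2. Size of the understatement.** The protocol gives no half-life, so t = 2 to 24 h is assumed, with linear, mono-exponential kinetics. Without a dose at 12 h, the 12-24 h area is the 0-12 h area times 2^(-12/t). Hence

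Day 19 AUC(0-24) / [2 x AUC(0-12),ss] = (1 + 2^(-12/t)) / 2.

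| t (h) | ratio | understatement |
|---|---|---|
| 2 | 0.508 | 49.2% |
| 4 | 0.5625 | 43.8% |
| 6 | 0.625 | 37.5% |
| 8 | 0.677 | 32.3% |
| 12 | 0.750 | 25.0% |
| 24 | 0.854 | 14.6% |

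The ratio is below 1 for every finite t, so only the size depends on the assumption.

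**3. Check with oral absorption and the planned samples.** A one-compartment model with first-order absorption (ka 0.5 and 1.5 per h, assumed) was run for the 12 twice-daily doses plus the Day 19 dose. The Day 19 0-24 h area divided by the two-dose 24 h area is 0.510 to 0.874. At the Table 3 times it is 0.504 to 0.873 (linear-up/log-down) or 0.522 to 0.877 (linear). From the same samples, 2 x AUC(0-12),ss recovers 0.987 to 1.001 of the two-dose area.

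**4. Dose consequence, only if the observed value were scaled to 18 µM.h.** Let x = 2^(-12/t). Two bounds apply to true daily exposure.

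- Bound A comes from the single-dose limit and the daily cap. If the top single dose D met its 18 µM.h limit over 0-24 h, its total area is at most 18/(1 - x²). At 140 mg a day, exposure is at most (140/D) x 18/(1 - x²). The numerator is 16.8 for D = 150 mg and 21 for D = 120 mg.
- Bound B comes from holding the observed Day 19 value at 18, which gives 36/(1 + x).

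| t (h) | A, 150 mg | A, 120 mg | B |
|---|---|---|---|
| 2 | 16.8 | 21.0 | 35.4 |
| 4 | 17.1 | 21.3 | 32.0 |
| 6 | 17.9 | 22.4 | 28.8 |
| 8 | 19.2 | 24.0 | 26.6 |
| 12 | 22.4 | 28.0 | 24.0 |
| 24 | 33.6 | 42.0 | 21.1 |

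A rises with t and B falls, so the worst case is where they meet.

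- 150 mg: 16.8 = 36(1 - x), so x = 0.533, t = 13.2 h and exposure is 36/1.533 = 23.5 µM.h.
- 120 mg: 21 = 36(1 - x), so x = 0.417, t = 9.5 h and exposure is 36/1.417 = 25.4 µM.h.

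With 150 mg as the top single dose, A stays at or below 18 up to t of about 6.1 h. With absorption (ka 0.5 and 1.5 per h) the maxima are 23.1 and 23.4 (150 mg), and 25.0 and 25.3 (120 mg).

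**The case against.** The strongest reply is that section 6.1.1.2 gives no calculation rule for this parameter, and that the steady-state label could itself imply two full intervals. Derivation detail of that kind often sits in the statistical analysis plan. Doubling is indeed a legitimate reading of the symbol, but it is not the one the protocol's definitions produce. Section 6.1.1.2 also writes out a formula for the accumulation ratio, so the protocol does fix derivations at this level.

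The food rules in sections 3.3.4 and 3.4.2 mention an evening dose in connection with Day 19. The dose total, the reference to a last dose followed by a 72 h stay, and the Day 19 row of Table 3 outweigh that wording.

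Several points do stand.

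- The 18 µM.h limit is applied to modelled predictions, and a model with two daily doses would be correct. No text says that the observed Day 19 area is scaled, although the stopping rule in 3.1.1.3 does not exclude it.
- The 23.5 and 25.4 µM.h figures combine a near-worst half-life, a top single dose exactly at its limit and the full 140 mg a day.
- A reader can recover daily exposure by doubling AUC(0-12),ss. The accumulation ratio uses 0-12 h areas and is unaffected by the missing evening dose.
- Both ethnic groups are measured in the same way and no hypothesis is tested.
- Under the once-daily fallback in section 3.2.1, the present meaning would be right.

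**Conclusion.** The concern holds. As written, the Day 19 AUC(0-24),ss is a one-dose area reported as 24-hour steady-state exposure on a two-dose regimen. The direction is certain for any finite half-life. The size is 49% to 15% for assumed half-lives of 2 to 24 h under linear, mono-exponential kinetics, and oral absorption changes it little.

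The harm lies mainly in the absolute exposure reported, much less in the comparison of Japanese and Caucasian volunteers. A breach of the exposure limit does not follow from the text. It would require scaling of the observed value, and even then the single-dose limit, the 140 mg cap and the Cmax,ss limit restrict it. It should be fixed, because the parameter is stated, it serves the primary objective, and the correct quantity is already being collected.

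**What to change.** In section 6.1.1.2 and the synopsis, define AUC(0-24),ss for twice-daily dosing as 2 x AUC(0-12),ss, or as a modelled 24 h area with two doses. State that this quantity is used wherever the 18 µM.h multiple-dose limit is checked (synopsis, 3.1, 3.1.1.3, 3.2.1 and 3.4.2). Relabel the observed Day 19 0-24 h area as a post-last-dose area without the steady-state suffix. Keep the present meaning only if once-daily dosing is adopted.

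AUC(0-12),ss is already a Day 19 parameter, so no samples or assays are added. The change is to wording, but section 5.4 requires a protocol amendment to be notified to or approved by the Ethics Committee. Reported daily exposure will be higher than the observed Day 19 0-24 h area.
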